5.8.1.3. Relationship between Pharmacokinetic Concentration and Efficacy

To explore the relationship between guselkumab serum concentrations and the efficacy endpoints, the analyses of the primary and secondary efficacy endpoints by trough concentrations, using quartiles, at Week 16, Week 24 and Week 48 will be presented graphically.

Additional relationships between the serum concentrations and the exploratory efficacy endpoints may be explored graphically.

5.8.1.4. Population Pharmacokinetic Analysis

If sufficient data are available, then population PK analysis using serum concentration-time data of guselkumab will be performed using nonlinear mixed-effects modeling. Details will be given in a population PK analysis plan and the results of the analysis will be presented in a separate report.

5.8.2. Immunogenicity

5.8.2.1. Immunogenicity Analysis

Unless otherwise mentioned, summaries of immunogenicity to guselkumab will be provided based on the Immunogenicity Analysis Set.

Serum samples will be screened for antibodies binding to guselkumab and the titer of confirmed positive samples will be reported.

The incidence and titers of antibodies to guselkumab will be summarized through Week 48 and through Week 152 for all participants who receive a dose of guselkumab and have appropriate samples for detection of antibodies to guselkumab (ie, participants with at least 1 sample obtained after their first dose of study intervention). The maximum titers of antibodies to guselkumab will be provided for participants who are positive for antibodies to guselkumab. These analyses will also be performed by baseline immunomodulator use (Yes, No).

Separate listings of participants who are positive for antibodies to guselkumab will be provided. The listing will contain intervention group, visit, serum guselkumab concentration at the visit, dose administered, baseline immunomodulators use (Yes or No), CDAI score at the visit, modified Rutgeerts score, SES-CD score at the visit, **CCI** -site reactions, and antibody status (titer and neutralizing antibodies status) for all visits, and cross over status (Yes or No). In addition, a list of antibodies to guselkumab status in participants who discontinued study intervention early will be provided.

The incidence of neutralizing antibodies (NAbs) to guselkumab will be summarized for participants who are positive for antibodies to guselkumab and have samples evaluable for NAbs to guselkumab.

5.8.2.2. Other Immunogenicity Analyses

To explore the relationship of antibodies to guselkumab status with serum guselkumab concentrations, and efficacy and safety, the following analyses may be performed as appropriate:

- Summary of median trough serum guselkumab concentrations over time by antibodies to guselkumab status
- Summary of primary and secondary efficacy endpoints by antibodies to guselkumab if sufficient participants have antibodies to guselkumab
- Summary of CCI -site reactions by antibodies to guselkumab status

5.8.3. Pharmacodynamics and Biomarkers

Changes in serum protein analytes and whole blood ribonucleic acid (RNA) obtained over time will be summarized by study intervention group. Associations between baseline levels and changes from baseline in select markers and response to study intervention will be explored. The biomarker analyses will characterize the effects of guselkumab to identify biomarkers relevant to study intervention, and to determine if these biomarkers can predict response to guselkumab.

Inflammatory pharmacodynamics markers (CRP and fecal calprotectin) will be evaluated and are discussed in further detail in Appendix 6.3. Analyses of serum biomarkers, whole blood RNA, peripheral blood mononuclear cells, stool biomarkers, and endoscopic biopsy will be reported in separate technical reports.

Planned biomarker analyses may be deferred if emerging study data show no likelihood of providing useful scientific information. Any biomarker samples received by the contract vendor or sponsor after the cutoff date will not be analyzed, and therefore, excluded from the biomarker analysis.

5.8.4. Health Economics

The data collected will be used to conduct exploratory economic analyses based on the FAS. The summaries of health economics will be performed for the main study period.

5.8.4.1. Medical Resource Utilization and Health Economics Data, Associated with Medical Encounters

Medical resource utilization and health economics data associated with medical encounters, will be collected in the CRF throughout the study.

- 1. Proportion of participants having any CD-related ER/hospitalizations and/or surgeries through Week 48.
- 2. Summary of duration of CD-related medical care encounters, including surgeries, and other selected procedures (inpatient and outpatient) (total days length of stay, including duration by wards; eg, intensive care unit)
- 3. Time to first CD-related ER/hospitalization and/or surgeries through Week 48.
- 4. Summary of duration of hospitalization (total days length of stay, including duration by wards; eg, intensive care unit)
- 5. Proportion of participants having any ER/hospitalizations and/or surgeries through Week 48
- 6. Time to first ER/hospitalization and/or surgeries through Week 48
- 7. Proportion of participants with a CD-related surgery through Week 48
- 8. Time to first CD-related surgery through Week 48
- 9. Summary of diagnostic and therapeutic tests and procedure by type through Week 48

5.8.4.2. Work Productivity and Activity Impairment-General Health

For the endpoints listed below, analysis will be based on the data as observed and the attributes and strategies for the ICEs will only be applied to Work Productivity and Activity Impairment

Questionnaire-General Health (WPAI-CD) endpoint:

1. Change from baseline in the WPAI at each post baseline visit through Week 152

WPAI-CD

The WPAI-CD is a validated instrument created as a patient-reported quantitative assessment of the amount of absenteeism, presenteeism, and daily activity impairment attributable to Crohn's disease. The WPAI-CD consists of 6 questions:

Q1) currently employed (working for pay)? (yes, no) If No, skip to Q6.

Q2) hours missed from work in the past 7 days due to Crohn's disease,

Q3) hours missed in the past 7 days from work for other reasons,

Q4) hours worked in the past 7 days,

Q5 the degree to which Crohn's disease affected work productivity while at work in the past 7 days,

Q6) the degree to which Crohn's disease affected activities outside of work in the past 7 days.

Four scores are derived.

- 1. percentage of absenteeism: 100*Q2/(Q2+Q4)
- 2. percentage of presenteeism (reduced productivity while at work): 100*Q5/10
- 3. an overall work impairment score that combines absenteeism and presenteeism: $100 + \{Q2/(Q2+Q4) + [(1-Q2/(Q2+Q4)) + (Q5/10)]\}$
- 4. percentage of impairment in activities performed outside of work: 100* Q6/10

Higher scores indicate greater impairment.

Note that for participants with answer='No' to Q1, only the 4th score (ie, percent activity impairment outside work due to CD) can be calculated.

5.8.5. Definition of Subgroups

The following subgroups will be evaluated for the primary endpoint in this study:

- 1. Demographics:
 - a. Age at baseline (\leq median age, > median age)
 - b. Sex (male, female)
 - c. Race (Caucasian, non-Caucasian)
 - d. Weight at baseline (\leq median body weight, > median body weight)
 - e. Center location [Americas (Canada, USA), APAC (Australia, South Korea, Taiwan), EMEA (Austria, Belgium, Czech Republic, France, Germany, Hungary, Israel, Italy, Netherlands, Poland, UK, Serbia, Spain), LATAM (Argentina, Brazil, Mexico)]

CONFIDENTIAL – FOIA Exemptions Apply in U.S.

Statistical Analysis Plan CNTO1959CRD3007

- 2. Baseline disease characteristics:
 - a. CD duration (\leq 5 years, > 5 years to \leq 15 years, or > 15 years)
 - b. Involved gastrointestinal areas (ileum, colon, ileum & colon)
 - c. number of CD-related prior surgeries (0, 1-2, >2)
 - d. CDAI score ($<150, \ge 150$)
- 3. Baseline CD-related concomitant medication usage and tumor necrosis factor (anti-TNF) history:
 - a. Oral corticosteroids (receiving, not receiving)
 - b. Oral corticosteroids and (6-MP, AZA, or MTX) (receiving, not receiving)
 - c. Oral corticosteroids or (6-MP, AZA, or MTX) (receiving, not receiving)
 - d. Prior biologic use (Yes, No)
- 4. Risk factors for recurrence of active CD:
 - a. Number of risk factors for recurrence of active CD (1, >1)
 - b. The qualifying surgery was the patient's second intra-abdominal operation for CD in the past 10 years (Yes, No)
 - c. The qualifying surgery was the patient's third (or more) intra-abdominal operation for CD (Yes, No)
 - d. The qualifying surgery was performed for a penetrating complication of CD (ie, an intraabdominal abscess, internal fistula, sinus tracts or intestinal perforation) (Yes, No)
 - e. The patient has any history of perianal fistulizing CD provided that this has not been active in the 3 months prior to study start (Yes, No)
 - f. Smoking statue (Y, N)
 - g. The patient has Kono-S (antimesenteric functional end-to-end handsewn) (Yes, No)
 - h. The patient has mesenterectomy (Yes, No)

Statistical Analysis Plan CNTO1959CRD3007

6. SUPPORTING DOCUMENTATION

6.1. Appendix 1 List of Abbreviations

ADA	anti-drug antibody
AE	adverse event
ALT/SGPT	alanine aminotransferase
ANCOVA	analysis of covariance
AST/SGOT	aspartate aminotransferase
ATC	anatomic and therapeutic class
AUC	area under the curve
BMI	body mass index
BSA	body surface area
CI	confidence interval
CL	total systemic clearance
Cmax	maximum concentration
CRF	case report form
CSR	Clinical Study Report
CTCAE	Common Terminology Criteria for Adverse Events
CV	coefficient of variation
DMC	Data Monitoring Committee
DPS	Data Presentation Specifications
ECG	Electrocardiogram
eCRF	electronic case report form
F (%)	absolute SC bioavailability
FAS	full analysis set
FDA	Food and Drug Administration
iARBM	Integrated Analytical Risk-Based Monitoring
ICH	International Conference on Harmonisation
IQ	Interquartile
IVRS	interactive voice response system
IWRS	interactive web response system
LLOQ	lower limit of quantification
LOCF	last observation carried forward
MedDRA	Medical Dictionary for Regulatory Activities
MRD	minimum required dilution
Nab	neutralizing antibodies
PD	pharmacodynamic(s)
PI	principal investigator
PK	pharmacokinetic(s)
PP	per protocol
QTL	Quality Tolerance Limit
SAE	serious adverse event
SAP	Statistical Analysis Plan
SD	standard deviation
SMQs	standardised MedDRA queries
TEAE	treatment-emergent adverse event
Tmax	time to maximum concentration
US NCI	United States National Cancer Institute
V	volume distribution
Vz	volume of distribution based on terminal phase
Vz/F	apparent volume of distribution based on terminal phase after extravascular administration
WHO	World Health Organization
WHO-DD	World Health Organization Drug Dictionary

6.2. Appendix 2 Changes to Protocol-Planned Analyses

6.3. Appendix 3 Demographics and Baseline Characteristics

Table 14 and Table 15 present the list of the demographic and baseline Crohn's disease variables that will be summarized by treatment group, and overall for the FAS.

Table 14: Demographic Variables

Continuous Variables	Summary Type
Age (years)	En di-tuil-uti- aith th -
Weight (kg)	Frequency distribution with the number and percentage of
Height (cm)	participants in each category.
BMI (kg/m^2)	participants in each category.
Categorical Variables	
Sex (male, female, unknown, undifferentiated)	
Race ^a (American Indian or Alaska Native, Asian (Japanese or Other	
Asian), Black or African American, Native Hawaiian or other Pacific	
Islander, White, Multiple)	
Ethnicity (Hispanic or Latino, not Hispanic or Latino)	
Region (North America, Western Europe, rest of world)	
Tobacco or nicotine use (non-user, prior user, current user)	
Alcohol use (never used, current user, former user)	

^aIf multiple race categories are indicated, the Race is recorded as 'Multiple'

Table 15: Baseline Disease Characteristic Variables

Continuous Variables	Summary Type
Crohn's disease duration (years)	
CDAI score	Description statistics (N. marsu
PRO-2 score (weighted sum of AP and SF subscores of CDAI)	Descriptive statistics (N, mean, standard deviation [SD], median
Days from surgery to randomization	and range [minimum and
IBDQ	maximum], and IQ range).
CRP	maximum], and iQ range).
Fecal Calprotectin	
Categorical Variables	
Crohn's disease complications (Intra-abdominal abscess, sinus	
tracts/perforations, fistula, structuring complications of CD, total or sub-	
total colectomy, partial bowel resection, perianal surgery, other CD related	
surgery, total parenteral nutrition)	Frequency distribution with the
Involved GI areas (Ileum, Colon, Ileum and Colon)	number and percentage of
Previous ADTs $(1, 2, > 2)$	participants in each category.
Primary nonresponse to at least one approved ADT (yes, no)	······································
Secondary nonresponse to at least one approved ADT (yes, no)	
Intolerance to at least one approved ADT (yes, no)	
PRO-2 score [Stool frequency \geq 4 and Abdominal pain \geq 2, Stool	
frequency \geq 4 and Abdominal pain \leq 2, Stool frequency \leq 4 and	
Abdominal pain ≥ 2]	
Fecal calprotectin > 250 mg/kg	
CRP >3 mg/L	
Fecal calprotectin > 250 mg/kg and CRP >3 mg/L	

^aIf multiple race categories are indicated, the Race is recorded as 'Multiple'

6.4. Appendix 4 Protocol Deviations and Quality Tolerance Limits (QTL)

In general, the following list of major protocol deviations (PDs) may have the potential to impact participants' rights, safety or well-being, or the integrity and/or result of the clinical study. Participants with major protocol deviations will be identified prior to database lock.

The following categories will be considered as major PDs:

- Received wrong treatment or incorrect dose
- Entered but did not satisfy criteria
- Received a disallowed concomitant treatment
- Developed withdrawal criteria but not withdrawn
- Other
 - Didn't cross over when met the cross over criteria
 - Cross over when not met the cross over criteria

Participants with a major protocol deviation through Week 48 will be summarized by category based on the FAS. A listing of participants who have major protocol deviations will be provided.

Participants having irregularities in study intervention administration will be summarized in more detail using sub-categories identified prior to unblinding (eg, participant receives study intervention administration outside of protocol window). In addition, participants with study intervention administration irregularities will be listed.

A listing of participants with protocol deviations related to COVID-19 by center and by category (major PD, minor PD) will be provided.

Quality Tolerance Limit (QTL) parameters and thresholds are defined and will be monitored in this study. QTL parameters will be summarized. More details are described in the Integrated Analytical Risk-Based Monitoring (iARBM) Plan.

6.5. Appendix 5 Prior and Concomitant Medications

Prior and Concomitant medications will be coded using the [World Health Organization Drug Dictionary (WHO-DD)]. Prior medications are defined as any therapy used before the day of first dose (partial or complete) of study intervention. Concomitant medications are defined as any therapy used on or after the same day as the first dose of study intervention, including those that started before and continue on after the first dose of study intervention.

Summaries of CD concomitant medications will be presented by ATC term and intervention group. Prior medications will be summarized by ATC term and intervention.

Summarized of CD medication history for the FAS will be summarized by treatment group:

- Summary of Concomitant Medications for CD at Baseline
 - Participants with 1 or more concomitant medications for CD (n, %)
 - Aminosalicylates (n, %)
 - Antibiotics (n, %)
 - Corticosteroids (including budesonide and beclomethasone dipropionate) (n, %)
 - Corticosteroids P.Eq dose (excluding budesonide and beclomethasone dipropionate) (mg/day)
 - Budesonide dose (mg/day)
 - Beclomethasone dirpropionate dose (mg/day)
 - Corticosteroids (duration of use)
 - Immunomodulators (6-MP/AZA/MTX) (duration of use)
 - Biologics (Infliximab, Adalimumab, Certolizumab Pegol, Vedolizumab, Ustekinumab, Risankizumab, biosimilars of Infliximab and Adalimumab)
- Summary of TNF Antagonist Therapy History by Number of TNF Antagonists (1, 2, 3) Received
 - Participants with inadequate initial response, loss of response, or intolerance to TNF antagonist
 - Participants with inadequate initial response to TNF antagonist
 - Participants with response followed by loss of response to TNF antagonist
 - Participants with intolerance to TNF antagonist
- Summary of Biologic Therapy History by Biologic (Infliximab, Adalimumab, Certolizumab Pegol, Vedolizumab, Ustekinumab, Risankizumab, biosimilars of Infliximab and Adalimumab)
 - Participants with inadequate initial response, loss of response or intolerance to biologic therapy
 - Participants with inadequate initial response to biologic therapy

- Participants with response followed by loss of response to biologic therapy
- Participants with intolerance to biologic therapy
- Summary of CD-related Non-biologic Medication History (History of Response to or Intolerance of Corticosteroids or 6-MP/AZA/MTX)
 - Participants with inadequate response, intolerance, or dependence
 - Participants with inadequate response
 - Participants intolerant
 - Participants dependent
- Summary of CD-related Biologic Medication History
 - Primary response, secondary nonresponse, or intolerance to
 - At least one anti-TNF
 - $\circ \geq 2$ anti-TNFs
 - o Anti-TNF only
 - o Ustekinumab
 - Ustekinumab only
 - Ustekinumab and at least one other biologic
 - o Vedolizumab
 - Vedolizumab only
 - Vedolizumab and at least one other biologic
 - o Risa
 - o Risa only
 - Risa and at least one other biologic

6.6. Appendix 6 Medical History

A summary of medical history of interest, as well as a summary of CD history and CD conditions of interest, and smoking status will be summarized for the FAS.

6.7. Appendix 7 Intervention Compliance

Randomized treatment versus actual treatment will be summarized using the FAS.

The doses in mg will be calculated based on administered volume (the actual volume administered after accounting for priming and flushing) as follows:

- For Placebo:
 - For induction dosing at Week 0:
 - CCI 1: dose $[mg] = (administered volume [mL]/1 mL) \times 0 mg$
 - CCl 2: dose $[mg] = (administered volume [mL]/1 mL) \times 0 mg$
 - For maintenance dosing starting at Week 8 then ^{CCI} through Week 144:
 - 1: dose $[mg] = (administered volume [mL]/1 mL) \times 0 mg$
- For Guselkumab:

0

- For induction dosing at Week 0:
 - \circ CCI 1: dose [mg] = (administered volume [mL]/1 mL) x 100 mg
 - CCl 2: dose $[mg] = (administered volume [mL]/1 mL) \times 100 mg$
- For maintenance dosing starting at Week 8 then ^{CCI} through Week 144:
 - \circ CCI 1: dose [mg] = (administered volume [mL]/1 mL) x 100 mg

6.8. Appendix 8 Adverse Events of Special Interest

Any newly identified:

- clinically significant infection tuberculosis (TB) events, invasive fungal infections, and hepatitis B reactivation
- newly identified malignancy
- hypersensitivity reaction
- congestive heart failure
- demyelinating disorders
- lupus-like syndrome

after the first study intervention administration are considered as AESI.

• Malignancy will be identified as AEs where the preferred perm is featured in the global Standardized MedDRA Queries (SMQ) dataset is SMQ='MALIGNANCIES (SMQ)' and SUB_SMQ1='MALIGNANT TUMOURS (SMQ)'

The following AEs will be identified and summarized as described in Section 5.7.2:

- Drug-related hepatic disorders will be identified by SMQs (narrow) MedDRA version 24.1 or current available version:
 - Select AE terms from dictionary with smq = "HEPATIC DISORDERS (SMQ)" and sub_smq1="DRUG RELATED HEPATIC DISORDERS - COMPREHENSIVE SEARCH (SMQ)" and scope="NARROW"

Identification of other AEs:

- AEs associated with anaphylaxis/serum sickness
 - AEs with one of the following dictionary-derived term in ADAE ADaM dataset, variable ADAE.AEDECOD:
 - ANAPHYLACTIC REACTION
 - ANAPHYLACTIC SHOCK
 - ANAPHYLACTOID REACTION
 - ANAPHYLACTOID SHOCK
 - TYPE I HYPERSENSITIVITY
 - "SERUM SICKNESS"
 - "SERUM SICKNESS-LIKE REACTION"

6.9. Appendix 9 Medications of Special Interest

The following will be considered as prohibited changes in CD medications for the ICE category 2 for all estimands:

- 1. Prohibited medications initiated after Week 0:
- Immunomodulatory agents except for AZA, 6-MP, or MTX (including, but not limited to, 6-thioguanine, cyclosporine, mycophenolate mofetil, tacrolimus, and sirolimus).
- Advanced therapy agents (including, but not limited to, additional TNFα antagonists, antiIL23 medications, natalizumab, ustekinumab, vedolizumab, rituximab).
- All experimental vaccines and medications, including those for CD (including, but not limited to upadacitinib, filgotinib, ozanimod, etrolizumab, and andecaliximab).
- Thalidomide or related agents.
- Total or partial parenteral nutrition
- IV and intramuscular corticosteroids
- Oral corticosteroids dose at a prednisone-equivalent dose above 20 mg/day, or 6 mg/day of budesonide, or 5 mg/day beclomethasone dipropionate.
- Live vaccines
- Participants must not receive guselkumab outside of the protocol or participate in any other clinical study with an investigational agent while in this study. Prior to termination of study participation, participants should complete evaluations for an ED visit.
- 2. Corticosteroids initiated or doses changed based on medical necessity as assessed by the investigator:
- Initiation of oral corticosteroids (including budesonide and beclomethasone dipropionate) due to worsening of CD.
- Increase in the dose of oral corticosteroids (including budesonide and beclomethasone dipropionate) above the baseline dose due to worsening of CD.
- Initiation of oral corticosteroids (including budesonide and beclomethasone dipropionate) due to reasons other than worsening CD for more than 28 days cumulatively between Week 0 and Week 48.
- Increase in the dose of oral corticosteroids (including budesonide and beclomethasone dipropionate) above the baseline dose due to reasons other than worsening of CD for more than 28 days cumulatively between Week 0 and Week 48.
- 3. Immunomodulator agents initiated from Week 0 through Week 48 or doses changed based on medical necessity as assessed by the investigator:
- Initiation of oral 6-MP/AZA due to worsening of CD.
- Initiation of oral, subcutaneous, or intramuscular MTX due to worsening of CD.
- Increase in the dose of oral 6-MP/AZA above the baseline dose due to worsening of CD.

- Increase in the dose of oral, subcutaneous, or intramuscular MTX above the baseline dose due to worsening of CD (within the same route).
- Any switch between 6-MP/AZA and MTX due to worsening of CD.
- 4. Antibiotics
- Initiation or change of antibiotics due to worsening CD.

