8.4.7. Hypersensitivity Reactions

Before any administration of study intervention at the study site, appropriately trained personnel and medications (eg, antihistamines, injectable epinephrine) must be available to treat hypersensitivity reactions, including anaphylaxis. All participants must be alert for or, when on site, observed carefully for signs and symptoms of a hypersensitivity reaction (eg, urticaria, pruritus, angioedema, wheezing, dyspnea, or hypotension). If a mild or moderate hypersensitivity reaction is observed, acetaminophen, nonsteroidal anti-inflammatory drugs, and/or diphenhydramine may be administered. Participants who experience serious adverse reactions related to an infusion must strongly be considered to be discontinued from further study intervention administrations.

In the case of a severe hypersensitivity reaction (eg, anaphylaxis), SC aqueous epinephrine, corticosteroids, respiratory assistance, and other proper resuscitative measures are essential and must be available at the study site where the infusions are being administered.

Participants who experience reactions suggestive of serum sickness (resulting in symptoms such as myalgia and/or arthralgia with fever and/or rash that are not representative of signs and symptoms of other recognized clinical syndromes) occurring 1 to 14 days after an infusion of study intervention, should be discontinued from further study intervention administrations. Note that these symptoms may be accompanied by other events including pruritus; facial, hand, or lip edema; dysphagia; urticaria; sore throat; and headache.

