5. 6.	Discontinuation of study intervention due to COVID-19 related reasons (excluding COVID-19 infection) Discontinuation of study intervention due to reasons other than those in ICE 3 or 5	and any data observed after the associated ICE event will be used for the analysis

Abbreviation: AE=adverse event; CD=Crohn's disease; COVID-19= Coronavirus disease 2019; ICE=intercurrent event

20

Intercurrent events in categories 1-4 will be handled by the composite strategy. The composite strategy assesses the treatment effects not only based on the variable measurements, but also based on ICEs. This estimand acknowledges that having an ICE in categories 1-4 is an unfavorable outcome. For participants experiencing ICEs in category 5 and 6, the treatment policy strategy will be used and considers the occurrence of ICE category 5 and 6 is irrelevant in defining the treatment effect and so observed values of the variable will be used, if available, regardless of the occurrence of ICE category 5 and 6.

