5.4.1.2.2. Estimand of Time to Disease Recurrence

Objective: To evaluate disease recurrence in participants treated with guselkumab versus placebo after surgery

Estimand Scientific Question of Interest: What is the difference in time to disease recurrence at the main database lock, and thus considered to have benefited from guselkumab versus placebo?

Study intervention:

- Experimental: Guselkumab ^{CCI} at Week 0 and then ^{CCI} at Week 8, then ^{CCI} thereafter through the end of the total study period.
- Control: Matched placebo CCI at Weeks 0 and 8 and then CCI thereafter through the end of the total study period.

Population: Participants with recent (<49 days) qualifying surgery and no evidence of active Crohn's disease postoperatively.

Variable: The time to disease recurrence (as defined above) or experiencing ICE 1-3 presented below.

CONFIDENTIAL – FOIA Exemptions Apply in U.S.

Summary Measure (Population-level summary): Difference in the time to disease recurrence (as defined above) or experiencing ICE 1-3 presented below between guselkumab group and the placebo group.

Intercurrent events and their corresponding strategies:

The following are the ICEs considered for this study:

Table 10: Intercurrent Events and Corresponding Analysis Strategies for Disease Recurrence at Main Database Lock

Int loc	ercurrent Events (between baseline and main database k)	Analysis Strategy for Intercurrent Events
1.	A CD-related surgery (with the exception of minor procedures such as drainage of a superficial abscess or seton placement, etc.)	Composite Strategy: Participants are considered having disease recurrence if they experience any of these ICEs, prior to main database lock, as
2.	A prohibited change in CD medication (details in Appendix 9 Medications of Special Interest)	reflected in the variable definition.
3.	Discontinuation of study intervention due to lack of efficacy or an AE of worsening CD	
4.	Discontinuation of study intervention due to COVID-19 related reasons (excluding COVID-19 infection)	Treatment Policy: ICE4 and ICE5 will be ignored, and any data observed after the
5.	Discontinuation of study intervention due to reasons other than those in ICE 3 or 4	associated ICE event will be used for the analysis.

Abbreviation: AE=adverse event; CD=Crohn's disease; COVID-19= Coronavirus disease 2019; ICE=intercurrent event

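### SAP Appendix 9 scores a live vaccine or a non-CD experimental product as endoscopic or disease recurrence, and its steroid entries need reconciling

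*SAP*

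**What the plan says.** ICE 2 in SAP 5.3.2.1 (Table 7), 5.4.1.2.1 (Table 9) and 5.4.1.2.2 (Table 10) is a prohibited change in CD medication. Appendix 9 (SAP 6.9) supplies its content: "The following will be considered as prohibited changes in CD medications for the ICE category 2 for all estimands".

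Item 1 of the appendix covers products started after Week 0. It includes live vaccines, "All experimental vaccines and medications, including those for CD", "IV and intramuscular corticosteroids" and "Oral corticosteroids dose at a prednisone-equivalent dose above 20 mg/day, or 6 mg/day of budesonide, or 5 mg/day beclomethasone dipropionate". None of these entries has a condition on indication or duration. Items 2 to 4 do state an indication. For oral steroids, item 2 includes "Initiation of oral corticosteroids (including budesonide and beclomethasone dipropionate) due to reasons other than worsening CD for more than 28 days cumulatively", counted between Week 0 and Week 48, with a parallel entry for dose increases.

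ICE 2 is composite. For the primary estimand, SAP 5.3.2.1 says: "This estimand acknowledges that having an ICE in categories 1-4 is an unfavorable outcome". For time to disease recurrence, Table 10 says: "Participants are considered having disease recurrence if they experience any of these ICEs, prior to main database lock".

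The Introduction of the SAP records that four participants were enrolled and that the planned analyses are kept for reference only.

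**The concern.** A composite strategy is meaningful when the event itself signals treatment failure. Starting a new CD drug does. Receiving a live vaccine, or an experimental product for another condition, says nothing about the anastomosis or the bowel. Read as written, a participant with an i0 score at the Week 48 ileocolonoscopy who had one live vaccine is an endoscopic recurrence, and also a disease recurrence in the time-to-event analysis.

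The same list also feeds the other secondary estimands. Such a participant fails the binary remission and pain endpoints and has an event for time to recurrence of symptoms. Disease recurrence is the most exposed endpoint, because its assumed rates are low (10% and 20%) and events accumulate to the main database lock.

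No planned analysis separates these events out. The supplementary estimand (SAP 5.3.2.2.1) widens the composite, the tipping-point analysis (5.3.5.1) varies only missing outcomes, and the modified-score analysis (5.3.5.2) keeps the same ICE strategy. SAP 5.3.3.1 summarises ICEs by type but not by sub-type within ICE 2.

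**Working it through.** **1. The entries against the documents' other rules**

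| Item 1 entry | Rule elsewhere |
|---|---|
| Live vaccines | Protocol 5.3 (items 5 and 6): a lifestyle restriction. Absent from the prohibited lists in Protocol 6.8.2 and SAP 1.2.1. |
| Experimental vaccines and medications, CD or not | Protocol 6.8.2 and SAP 1.2.1: experimental or investigational medications for CD only. |
| IV/intramuscular steroids, and oral steroids above the stated doses, any indication or duration | Item 2: non-CD oral steroids after more than 28 cumulative days, Week 0 to Week 48. SAP 5.4.1.1: the steroid criterion for disease recurrence requires treatment of CD, more than one week, and endoscopic evidence. |

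The first two rows show a category broader than its own name and broader than the lists it should implement. The third row shows entries whose interaction is not stated.

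**2. The plan's own figures**

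Inputs from SAP Section 3: 185 per arm, two-sided alpha 0.05, 50% v 30%. For a two-proportion test with pooled variance and no continuity correction:

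- null SE = √(2 × 0.40 × 0.60 / 185) = 0.0509
- alternative SE = √((0.25 + 0.21) / 185) = 0.0499
- power = Φ((0.20 − 1.96 × 0.0509) / 0.0499) = 97.8%, against 97.7% stated.

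Disease recurrence, 20% v 10%: HR = ln(0.90)/ln(0.80) = 0.472. With the stated accrual pattern, 30 months in total and 15% annual dropout, reading the rates at 12 months gives about 76 events. Schoenfeld power is Φ(0.750 × √76.2 / 2 − 1.96) = 90.6%, against 90.0% stated. Reading the rates at exactly Week 48 gives 92.4%.

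**3. Illustrative dilution**

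The documents give no rate for non-CD Appendix 9 events. Let q be an assumed share per arm with any such event, independent of true recurrence.

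Primary: new rate = p + (1 − p)q, so with equal q the difference is 0.20 × (1 − q).

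| q | Placebo | Guselkumab | Difference | Power |
|---|---|---|---|---|
| 0 | 50.0% | 30.0% | 20.0 points | 97.8% |
| 2% | 51.0% | 31.4% | 19.6 points | 97.2% |
| 5% | 52.5% | 33.5% | 19.0 points | 96.1% |

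With unequal q the effect can go either way. At 2% placebo and 5% guselkumab the difference is 51.0 − 33.5 = 17.5 points. At 5% and 2% it is 52.5 − 31.4 = 21.1 points.

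Disease recurrence: add −ln(1 − q) to each cumulative hazard.

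- q = 2%: (0.1054 + 0.0202)/(0.2231 + 0.0202) = 0.52
- q = 5%: (0.1054 + 0.0513)/(0.2231 + 0.0513) = 0.57

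If q is a 12-month rate that continues to database lock, power falls from 90.6% to 86.0% and 78.6%. On the Week 48 reading it falls from 92.4% to 88.3% and 81.3%.

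**The case against.** The strongest reply concerns steroids, and most of it stands. Protocol 6.8.1 says that starting or increasing IV or oral corticosteroids is treatment failure and leaves the full criteria to the SAP; SAP 1.2.1 repeats the treatment-failure rule. Steroids in ICE 2 are therefore not an SAP invention, although 6.8.1 speaks of rescue for CD. Counting high-dose or parenteral steroids whatever the indication is a defensible trade-off: they may affect CDAI and mucosa, and the rule does not depend on a recorded reason. A reader might infer that items 1 and 2 contradict each other. The documents do not establish this. Item 2 does not say that non-CD oral steroids count only after 28 days, and the items can be read as two tiers, one by dose and one by duration. What remains is that the SAP does not say so.

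A reader might also infer bias against guselkumab, because Protocol 8.4.7 says that in a severe hypersensitivity reaction "corticosteroids, respiratory assistance, and other proper resuscitative measures are essential". That section requires steroids to be available. Protocol 2.3.1 reports such reactions from postmarketing experience, without a rate, and no document compares arms.

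On vaccines, the reply is that live vaccination is barred during the study (Protocol 5.3), planned live vaccination is an exclusion (5.2, criterion 18), and receipt of a disallowed treatment is already a major deviation (SAP Appendix 4). That makes the events rare. It does not make them recurrences. Nor does the name of ICE 2 limit the list to CD treatment: a live vaccine cannot fit that reading, and the experimental-product entry expressly extends beyond CD.

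**Conclusion.** The point holds for live vaccines and for experimental products not given for CD: as written, ICE 2 misclassifies these participants as recurrences. For steroids it holds only as a need to state how the entries fit together.

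The size is illustrative. At an assumed 2-5% per arm the primary endpoint barely moves (20.0 to 19.6-19.0 points), while the disease-recurrence HR moves from 0.47 to 0.52-0.57. These figures assume independence from true recurrence and equal rates in both arms, and q covers every non-CD event under Appendix 9. The vaccine and experimental entries alone would probably contribute less, since live vaccines are barred. A reader might take the figures as a threat to the primary result; power of at least 96.1% across that range does not support this. Any difference between arms is unproven.

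The defect is in the plan as designed. With four participants and the analyses retired, it has no practical effect on this trial's results.

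**What to change.** In Appendix 9 item 1:

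- Delete live vaccines from ICE 2 and report them as protocol deviations only, under SAP Appendix 4.
- Limit the experimental-product entry to agents given to treat CD, as in Protocol 6.8.2 and SAP 1.2.1. The last entry of item 1, on taking part in any other study with an investigational agent, needs the same limit for ICE 2; otherwise it brings non-CD products back in.

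For steroids, reconcile item 1, item 2 and the criterion in SAP 5.4.1.1. State which item governs a short course given for a reason other than CD, and what applies after Week 48. Moving all non-CD steroid use under item 2 would not be enough, because its 28-day rule stops at Week 48 while time to disease recurrence runs to the main database lock.

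Report ICE 2 by sub-type and arm, so that a reader can see what drives the composite.

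The cost is SAP wording and one extra tabulation. Protocol 6.8 already has the reason for use recorded for every concomitant medication, so no new data are needed. The limit on experimental products will rest on that recorded reason. These changes affect outcome classification, not what participants may receive.
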